1. INTRODUCTION

This SAP has been developed after review of the clinical study protocol (Final Version 1.0 dated 09 December 2020) and electronic case report form.

This SAP describes the planned analysis of the pharmacokinetic (PK), and safety and tolerability data from this study. A detailed description of the planned TFLs to be presented in the clinical study report (CSR) is provided in the accompanying TFL shells document.

In general, the analyses are based on information from the protocol, unless they have been modified by agreement with Loxo Oncology, Inc. A limited amount of information about this study (eg, objectives, study design) is given to help the reader's interpretation. This SAP must be finalized prior to the lock of the clinical database for this study. When the SAP and TFL shells are approved, they will serve as the template for this study's CSR.

This SAP supersedes any statistical considerations identified in the protocol; where considerations are substantially different, they will be so identified. If additional analyses are required to supplement the planned analyses described in this SAP, they may be performed and will be identified accordingly in the CSR. Any substantial deviations from this SAP will be agreed with Loxo Oncology, Inc. and identified in the CSR.

This SAP is written with consideration of the recommendations outlined in the International Conference on Harmonisation (ICH) E9 guideline *Statistical Principles for Clinical Trials* and ICH E3 guideline *Structure and Content of Clinical Study Reports*.^{1,2}

The document history is presented in [Appendix 1](#).

2. STUDY OBJECTIVES

2.1. Primary Objective

The primary objective of the study is to assess the effect of multiple oral doses of LOXO-305 on the PK of single oral doses of caffeine (cytochrome P450 [CYP]1A2 substrate), S-warfarin (CYP2C9 substrate), and omeprazole (CYP2C19 substrate) in healthy subjects.

2.2. Secondary Objective

The secondary objective of the study is to assess the safety and tolerability of multiple oral doses of LOXO-305 when administered alone, and coadministered with a single oral dose of probe drug cocktail.

3. STUDY ENDPOINTS

3.1. Primary Endpoints

The following PK parameters will be calculated whenever possible, based on the plasma concentrations of caffeine/paraxanthine, omeprazole, S-warfarin, and LOXO-305 (as appropriate):

- area under the concentration-time curve from hour 0 to 24 hours postdose (AUC₀₋₂₄)
- area under the concentration-time curve from hour 0 to the last measurable concentration (AUC_{0-t})
- area under the concentration-time curve from hour 0 extrapolated to infinity (AUC_{0-inf})
- percentage extrapolation for AUC_{0-inf} (%AUC_{extrap})
- apparent systemic clearance (CL/F)
- apparent plasma terminal elimination half-life (t_{1/2})
- maximum observed plasma concentration (C_{max})
- time to maximum observed plasma concentration (t_{max})
- apparent terminal elimination rate constant (λ_z)
- apparent volume of distribution at the terminal phase (V_z/F))
- mean residence time extrapolated to infinity (MRT_{inf})
- AUCratio of paraxanthine to caffeine ([MRAUC]; paraxanthine only).

3.2. Secondary Endpoints

Safety and tolerability will be assessed by monitoring adverse events (AEs), performing physical examinations and clinical laboratory evaluations, measuring vital signs, and recording 12-lead electrocardiograms (ECGs).

4. STUDY DESIGN

This is a Phase 1, open-label, 2-period, fixed-sequence drug-drug interaction study to investigate the effect of multiple oral doses of LOXO-305 on the PK of single oral doses of caffeine (CYP1A2 substrate) and its metabolite paraxanthine, S-warfarin (CYP2C9 substrate), and omeprazole (CYP2C19 substrate) in healthy subjects.

In Period 1, Day 1, 200 mg caffeine (tablet), 40 mg omeprazole (capsule), and 10 mg warfarin (tablet) administered as a single dose of probe drug cocktail, along with 10 mg vitamin K (tablets), will be administered in the morning following a fast of at least 10 hours predose and 2 hours postdose. Blood samples for concentrations of the substrates (caffeine/paraxanthine, omeprazole, and S-warfarin) in plasma will be collected predose through 120 hours postdose on Day 1. Of these samples, samples will be analyzed for concentrations of caffeine/paraxanthine from predose through 24 hours postdose, for concentrations of omeprazole [REDACTED], and for concentrations of [REDACTED].

There will be a washout period of 5 days between administration of the probe drug cocktail on Day 1 and the first dose of LOXO-305 on Day 6.

[figure not shown]
In Period 2, on Days 6 through 19, oral doses of 200 mg LOXO-305 will be administered once daily (QD) for 14 consecutive days in the morning at the actual time of the Day 1 probe drug cocktail dosing (\pm 1 hour). On Day 15, LOXO-305 will be coadministered with 200 mg caffeine (tablet), 40 mg omeprazole (capsule), and 10 mg warfarin (tablet) administered as a single dose of probe drug cocktail, along with 10 mg of vitamin K (tablets) at the actual time of the Day 1 probe drug cocktail dosing (\pm 1 hour) following a fast of at least 10 hours predose and 2 hours postdose. On Days 7 through 11, and Days 13, 14, 16, 18, and 19, subjects will fast for at least 2 hours predose and 1-hour postdose. On Days 6, 12, and 17 where clinical laboratory evaluations are performed, subjects will fast for at least 8 hours predose and 1 hour postdose. Blood samples for concentrations of LOXO-305 in plasma will

CCI

CCI. Samples collected CCI. CCI LOXO-305 dosing CCI. Blood samples for concentrations of the substrates (caffeine/paraxanthine, omeprazole, and S-warfarin) in plasma will be CCI; of these samples, samples will be analyzed for concentrations of caffeine/paraxanthine from CCI, for concentrations of omeprazole CCI, and for concentrations of CCI.

A schematic of the study design is presented in [Figure 1](#).

Figure 1: Study Design

EOT= end of treatment; ET = early termination; ICF = informed consent form.

The start of the study is defined as the date the first subject who is enrolled in the study signed an Informed Consent Form (ICF). Note that enrolled subjects are defined as those subjects who are assigned to receive a dose of study drug; this definition excludes screen failure subjects. Replacement subjects may be enrolled only if deemed necessary by the Sponsor.

Subjects who are determined to be screen failures are permitted to be re-screened if the Investigator (or designee), with agreement from the Sponsor, feels that the subject may meet

eligibility criteria upon re-screen. Re-screened subjects will be provided a new subject number.

To assess their eligibility to enter the study, potential subjects will be screened within 34 days (Days -35 to -2) and be admitted to the Clinical Research Unit (CRU) on Day -1 (Check-in).

Subjects will be confined at the CRU from the time of Check-in (Day -1) until End of Treatment (EOT) on Day 23 upon completion of all PK and safety assessments or Early Termination (ET) if the subject discontinues. Dosing of probe drug cocktail will occur on Day 1 and Day 15 and dosing of LOXO-305 will occur on Days 6 through 19. A follow-up phone call will occur for all subjects who received at least 1 dose of study drug (including subjects who are terminated early) 7 days (\pm 2 days) after EOT or ET. The duration of participation is expected to be approximately 67 days (Screening through follow-up phone call).

In this study, physical examinations, 12-lead ECGs, vital sign measurements, How Do You Feel? inquiries, clinical chemistry panel, coagulation parameters, hematology panel, urinalysis, and recording of concomitant medications will be performed at specified times during the study.

AEs and serious AEs (SAEs) will be collected beginning at informed consent. AEs will be reported throughout the study (ie, from signing of the ICF until End of Study [EOS], or until ET if the subject discontinues from the study and does not complete a follow-up phone call), either as subject medical history (if the event is reported as beginning prior to signing of the ICF or if the event occurs prior to study drug administration on Day 1 and is assessed as not related to study procedures by the Investigator [or designee]) or as AEs (if the event occurs after signing of the ICF but prior to study drug administration on Day 1 and is assessed as related to study procedures by the Investigator [or designee], or if the event occurs after study drug administration on Day 1 through EOT or ET regardless of relationship to study drug). From EOT or ET through EOS, only AEs assessed as related to study drug by the Investigator (or designee) are to be reported. All SAEs that develop from the time of ICF signing until EOS (or ET, if the subject discontinues from the study and does not complete a follow-up phone call) are to be reported. Study completion is defined as the time of the last subject's follow-up.

5. SAMPLE SIZE JUSTIFICATION

Up to **[REDACTED]** healthy adult male and female subjects (women of non-childbearing potential only) will be enrolled. The sample size chosen for this study was selected without statistical considerations but is consistent with previous studies of a similar design. Up to **[REDACTED]** subjects are anticipated to be sufficient to provide a reliable estimate of the magnitude and variability of the interaction. Replacement subjects may be enrolled only if deemed necessary by the Sponsor. Every attempt will be made to enroll at least 4 subjects of each sex in the study.

6. STUDY TREATMENTS

The study treatment sequence name and ordering to be used in the TFLs are presented in [Table 1](#).

Table 1: Presentation of Study Treatment Sequence in TFLs

Study Treatment Sequence Label
Probe Drug Cocktail (D1-5)/ 200 mg LOXO-305 QD (D6-14)/ 200 mg LOXO-305 QD + Probe Drug Cocktail (D15-19)/ 200 mg LOXO-305 QD (D20)

QD = once daily; TFL = table, figure, and listing.

Error! Reference source not found. shows a list of the PK treatment labels and ordering that will be used in the TFLs.

Table 2: Pharmacokinetic Treatment Labels

Study Treatment Labels	Order in TFLs
200 mg caffeine	1
200 mg LOXO-305 QD + 200 mg caffeine	2
40 mg omeprazole	3
200 mg LOXO-305 QD + 40 mg omeprazole	4
10 mg warfarin	5
200 mg LOXO-305 QD + 10 mg warfarin	6
200 mg LOXO-305 QD	7

QD = once daily; TFL = table, figure, and listing.

The study treatment names and ordering to be used in the TFLs are presented in [Table 3](#).

Table 3: Presentation of Study Treatment Labels in TFLs (Safety)

Study Treatment Labels	Order in TFLs
Probe Drug Cocktail*	1
200 mg LOXO-305 QD	2
200 mg LOXO-305 QD + Probe Drug Cocktail*	3

QD = once daily; TFL = table, figure, and listing.

*200 mg caffeine + 40 mg omeprazole + 10 mg warfarin + 10 mg Vitamin K

All treatments described above are the planned treatments. The TFLs will reflect the actual treatments received.

7. DEFINITIONS OF POPULATIONS

Any protocol deviations will be considered prior to database lock for their importance and taken into consideration when assigning subjects to populations.

7.1. All Subjects Population

The all subjects population will consist of all subjects who signed the ICF and had any study assessment recorded in the database per the protocol.

7.2. Safety Population

The safety population will consist of all subjects who have received at least 1 dose of study drug (probe cocktail drugs and/or LOXO-305). Subjects will be classified into groups based on actual treatment received.

7.3. Pharmacokinetic Population

The PK population will consist of all subjects who have received a dose of LOXO-305 or the probe cocktail drugs, have at least 1 quantifiable plasma concentration, and for whom at least 1 PK parameter can be computed. A subject may be excluded from the PK summary statistics and statistical analysis if the subject has an AE of vomiting that occurs at or before 2 times the median t_{max} . The impact of protocol deviations on the PK population will be evaluated on a case-by-case basis.

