1.5. Study Rationale

The objective of DDI studies is to determine whether potential interactions between an investigational drug and other drugs exist. Drug-drug interaction studies have an important role in drug development,⁹ and this study is being performed as part of the development program for LOXO-305.

LOXO-305 showed no detectable inhibition (IC_{50} **CCI** μ M) of CYP1A2, CYP2B6, CYP2C19, and CYP2D6, and weak inhibition of CYP2C8, CYP2C9, and CYP3A4 with inhibitory constant (K_i) values ranging from **CCI** μ M in human liver microsomes. After pre-incubation of microsomes with LOXO-305 and nicotinamide adenine dinucleotide phosphate for 30 minutes prior to addition of CYP450 probe substrate, the CYP3A4 inhibitory potency of LOXO-305 was increased, suggesting the potential for time-dependent inhibition of CYP3A4. Further kinetic evaluation confirmed that LOXO-305 is a time-dependent inhibitor of CYP3A4 with a K_i value of **CCI** μ M and a k_{inact} (maximal inactivation rate constant) value of **CCI** $.15\text{ h}^{-1}$ resulting in a C_{inact} value (inactivation clearance) of $8.64\text{ min}^{-1}\text{ mM}^{-1}$.

In an in vitro hepatocyte assay, LOXO-305 induced mRNA for CYP3A4, CYP3A5, CYP2B6, and CYP2C19. For both CYP2B6 and CYP2C19, an increase in activity was seen. For CYP3A4, LOXO-305 did not cause an increase in activity, likely due to concurrent inhibition of CYP3A4 by LOXO-305. LOXO-305 caused a decrease in mRNA for CYP1A2 but did not lead to a reduction of CYP1A2 activity. In the study, CYP2D6, CYP2C8, and CYP2C9 mRNA were not induced.

LOXO-305 may have the potential to raise plasma concentrations of drugs that are substrates of CYP2C8, CYP2C9, and CYP3A4 or lower plasma concentrations that are metabolized by CYP1A2, CYP2B6, CYP2C19, or CYP3A4. This study is designed to determine the effect of LOXO-305 on the PK of caffeine (CYP1A2 substrate), S-warfarin (CYP2C9 substrate), and omeprazole (CYP2C19 substrate). The effects of LOXO-305 on the PK of other CYP450 substrates will be explored in separate clinical studies. Caffeine, warfarin, and omeprazole are commonly used as index substrates for CYP450 enzymes in DDI studies.⁹

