8.2. Analysis Populations

The **PK Population** will consist of all subjects who have received a dose of LOXO-305 or the probe cocktail drugs, have at least 1 quantifiable plasma concentration, and for whom at least 1 PK parameter can be computed. A subject may be excluded from the PK summary statistics and statistical analysis if the subject has an AE of vomiting that occurs at or before t_{max} . The impact of protocol deviations on the PK population will be evaluated on a case-by-case basis.

The **Safety Population** will consist of all subjects who have received at least 1 dose of study drug (probe cocktail drugs and/or LOXO-305). Subjects will be classified into groups based on actual treatment received.

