8.5.1.4. Treatment of Outliers in Pharmacokinetic Analysis

If a value is considered to be anomalous due to being inconsistent with the expected PK profile, it may be appropriate to exclude the value from the PK analysis. However, the exclusion of any data must have strong justification and will be documented in the CSR.

Any quantifiable predose concentration value will be considered anomalous and set to missing for the PK analysis.

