8.5.3. Pharmacokinetic Statistical Methodology

All PK concentrations and parameters will be listed.

Summary tables, mean (+ standard deviation [SD]) figures, overlaying individual figures, and individual figures by analyte and time postdose will be provided for plasma PK concentrations. All PK concentration figures will be produced on both linear and semi-logarithmic scales, with the exception of figures across all days, which will be produced on the linear scale only. The +SD bars will only be displayed on the linear scale.

Summary tables by treatment will be provided for all PK parameters, with the exception of diagnostic regression-related PK parameters. Summary statistics (n, Mean, SD, CV, minimum, median, maximum, geometric mean [Geom Mean] and geometric CV [Geom CV]) will be calculated for plasma LOXO-305, caffeine, paraxanthine, omeprazole and S-warfarin

PK parameters. Excluded subjects will be listed in the PK parameter tables, but will be excluded from the statistical analysis and summary statistics and noted as such in the tables.

A statistical analysis will be conducted to investigate the drug-drug interaction on the PK of the following comparisons:

- LOXO-305 plus caffeine (test) versus caffeine alone (reference) To test the drug-drug interaction on the PK of caffeine and paraxanthine
- LOXO-305 plus omeprazole (test) versus omeprazole alone (reference)
- LOXO-305 plus warfarin (test) versus warfarin alone (reference)

The natural log-transformed³ PK parameters (AUC_{0-t} , $\text{AUC}_{0-\text{inf}}$, C_{\max} , and MRAUC for paraxanthine only) will be analyzed using a mixed model.⁴ The model will include actual treatment as a fixed effect, and subject as a random effect.

For each PK parameter separately, the least squares mean (LSM) for each treatment, difference in LSMs between the test and reference treatments, and corresponding 90% confidence interval (CI) will be calculated; these values will then be exponentiated to give the geometric least squares mean, geometric mean ratios, and corresponding 90% CI.

Additionally, the pooled estimate (across all treatments) of the within-subject CV will be calculated, and residual plots will be produced to assess the adequacy of the model(s) fitted.

Examples of the SAS code that will be used are as follows:

Mixed Model Analysis

```
proc mixed data = <data in>;
  by parcatln parcat1 paramn param;
  class trtan usubjid;
  model lpk = trtan / cl residual ddfm = kr2;

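### Does the optional vomiting exclusion in SAP 7.3, which names no analyte or dose, leave the probe-drug ratios open to choice?

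*SAP*

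**What the plan says.** Protocol 8.2 and SAP 7.3 both make the exclusion optional and apply it to the subject. In the protocol, "A subject may be excluded from the PK summary statistics and statistical analysis if the subject has an AE of vomiting" at or before t_max. In the SAP the subject may be excluded if he or she "has an AE of vomiting that occurs at or before 2 times the median" t_max. Neither names an analyte, a dose or a period.

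SAP 1 settles which text governs: "This SAP supersedes any statistical considerations identified in the protocol". It adds that substantial differences will be identified. SAP 10 reports no significant changes.

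On dosing, SAP 4 states: "Dosing of probe drug cocktail will occur on Day 1 and Day 15"; LOXO-305 is given on Days 6 to 19. SAP 6, Table 2, which "shows a list of the PK treatment labels and ordering that will be used in the TFLs", has separate labels for each probe alone, each probe with LOXO-305, and LOXO-305 alone.

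On exclusions, SAP 8.5.1.4, which deals with anomalous values, says "the exclusion of any data must have strong justification and will be documented in the CSR". SAP 8.5.3 says "Excluded subjects will be listed in the PK parameter tables", with their omission from the analysis noted there.

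**The concern.** Three terms are open in SAP 7.3.

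- **Which median.** Four probe analytes in two treatments plus LOXO-305 give 4 × 2 + 1 = 9 candidate medians.
- **Which dose.** There are 15 dosing days (Day 1 and Days 6 to 19), and 13 of them are LOXO-305 alone. Read literally, vomiting after any of these could remove a subject from every probe comparison.
- **Keep or drop.** The rule is permissive and gives no criterion. Exclusion has to be justified; retention does not.

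The study is open-label, and if the median is the study's own, the window is not known until concentrations are. A Day 15 profile kept after loss of dose lowers the ratio and could resemble induction; a kept Day 1 profile raises it and could resemble inhibition. With at most 16 subjects, one profile has visible weight in a primary comparison. The wider window than in Protocol 8.2, not listed in SAP 10, adds to the impression that the rule was left loose.

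**Working it through.** The plan gives no figure for this rule, so there is none to reproduce. The check has three parts.

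**1. Do other sections supply the missing terms?**

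- *Median.* SAP 8.5.1 derives t_max for each analyte, and SAP 8.5.3 summarises PK parameters by treatment. Each analysis therefore has its own median. The nine medians serve different analyses and do not compete as versions of one rule.
- *Dose.* SAP 8.6.1 calculates onset of treatment-emergent events from the last dose and assigns each event to a treatment. An event from the Day 6 dose until the Day 15 dose belongs to LOXO-305 alone. Events on Days 16 to 19 carry the combination label, but their onset is still counted from that day's dose. Day 15 and Day 16 doses are each within 1 hour of the Day 1 clock time, so they are at least 24 − 2 = 22 hours apart. Vomiting on Day 16 could fall in a probe's window only if that probe's median t_max were at least 22 / 2 = 11 hours.
- *Traceability.* All adverse events are listed with onset time (SAP 8.6.1), all concentrations and parameters are listed, and exclusions are noted (SAP 8.5.3). A reader can compare each onset with twice the median and see whether the profile was kept. Only a written reason for keeping it is absent.

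**2. How far does keep or drop move the ratio?**

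With complete pairs, the treatment contrast in the SAP's mixed model is the mean within-subject log difference. Assumptions, none from the documents: true ratio 1.00, within-subject CV 20%, and one of n = 16 subjects loses a fraction f of a probe dose on Day 15. Put d = ln(1 − f).

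- Kept: mean shift d/16; variance of log differences 2·ln(1 + CV²) + d²/16; half-width t(0.95, 15)·√(variance/16).
- Dropped: half-width t(0.95, 14)·√(2·ln(1 + CV²)/15).

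Here 2·ln(1.04) = 0.0784. At f = 0.5, d = −0.693, the shift is −0.0433 and the variance is 0.0784 + 0.0300 = 0.1085. The half-width is 1.753 × 0.0823 = 0.144.

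| Handling | Ratio | 90% CI |
|---|---|---|
| Dropped (n = 15) | 1.00 | 0.88–1.14 |
| Kept, 25% lost | 0.98 | 0.87–1.11 |
| Kept, 50% lost | 0.96 | 0.83–1.11 |
| Kept, 80% lost | 0.90 | 0.73–1.12 |

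The same event on Day 1, kept at 50% lost, gives 1.04 (0.90–1.21). For CV 15% to 30%, the lower limit is 0.91 to 0.83 if dropped, 0.85 to 0.79 if kept at 50% lost, and 0.74 to 0.70 if kept at 80% lost.

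Dropping the profile or the whole subject makes almost no difference. In 200 simulated trials fitted with the mixed model (between-subject CV 50%, within-subject CV 25%, 75% lost), the average ratio was 0.912 kept, 0.997 with the profile dropped and 0.997 with the subject dropped. Losing a subject needlessly after a LOXO-305-only dose costs precision: t(0.95, n − 1)·√(2/n) rises from 0.620 (n = 16) to 0.643 (n = 15), which is 3.8%.

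**3. How likely is the event?**

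Protocol 1.4 gives the healthy-volunteer LOXO-305 doses as 30 + 63 + 24 + 9 + 195 = 321. Protocol 1.4.1 reports vomiting in one volunteer, taken here as one dose.

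- Day 15: 1 − (320/321)^16 = 4.9%.
- The 13 × 16 = 208 LOXO-305-only doses: 1 − (320/321)^208 = 47.7%, with 95% limits of 1.6% to 97%.

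These rates count vomiting at any time, whereas the rule needs it inside the window. The closest prior study (15 volunteers, 13 daily 200 mg doses) lists no vomiting in its preliminary data. The cocktail's own effect on vomiting is not given.

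On the log scale, the expected Day 15 shift is 0.049 × 0.0433 = 0.2% at 50% lost and 0.049 × 0.1006 = 0.5% at 80% lost.

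**The case for a change.** The strongest case for a change is that none of the neighbouring rules is a PK-exclusion rule. SAP 8.6.1 concerns adverse-event reporting. The pre-lock review in SAP 7 covers protocol deviations, and vomiting need not be one. The justification sentence in SAP 8.5.1.4 concerns anomalous values. A single event would therefore call for an unplanned choice in a primary comparison, and low exposure is no neutral guide to that choice, because induction also lowers exposure. A few sentences would close the gap, and no analysis with and without the profile is planned.

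The textual part of this stands: the wording is incomplete, the two windows differ, and a kept profile with a large loss would matter. The rest carries less weight.

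- Onset time, which does not depend on exposure, is listed and is what an analyst would apply.
- A small loss barely moves the ratio. A large loss inside the window is the case in which an analyst using this rule would drop the profile.
- The argument that a kept profile biases toward the expected result fails. Protocol 1.5 says LOXO-305 may "lower plasma concentrations that are metabolized by CYP1A2, CYP2B6, CYP2C19, or CYP3A4", but it also reports reduced CYP1A2 mRNA, and Protocol 3.2 describes down-regulation of CYP1A2 and weak inhibition of CYP2C19. No single direction is supported for caffeine or omeprazole.
- The SAP sets no no-effect boundary, so no planned decision turns on the interval, and SAP 8.1 already asks for caution because the sample size was not based on power.
- A window based on the study's own median is unknown before the data under any wording that keeps this rule.

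**Conclusion.** No change to the plan is needed. SAP 7.3 leaves detail out, but the ordinary reading is sensible and fits the rest of the SAP: each probe's own median t_max, timed from the cocktail dose, with the compromised profile dropped. Profile-level and subject-level exclusion give nearly the same ratio. SAP 1 already makes the SAP window govern, so listing the difference from Protocol 8.2 in SAP 10 would change no result; whether an optional window is a significant change is a matter of judgement.

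The size is a ratio of about 0.96 in place of 1.00 if one of 16 Day 15 profiles with half its dose lost were kept, and 0.90 with 80% lost. This rests on assumed dose losses and an assumed CV of 20%. The 5% chance of a Day 15 event rests on one vomiting case and is therefore imprecise. If an event occurs, the planned listings let a reader identify it and repeat the comparison without the profile.
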